2.2 Study Rationale

Mutations of BRAF V600E have been identified at a high frequency in melanoma, PTC, colorectal and ovarian cancers. Such mutations have also been reported in some rare cancers such as ATC, HCL, GIST, NSGCT/NGGCT, BTC, MM, ASI (including periampullary and ampullary), WHO Grade 1 and 2 gliomas and WHO Grade 3 and 4 (high-grade) gliomas. These rare cancers have an incidence rate in the US ranging between 0.07 to 6.3 per 100,000 and have a frequency of BRAF V600E mutations ranging between 3% in WHO Grade 3 and 4 glioma to 90% in HCL (refer to Table 1) [Caronia, 2011; Tiacci, 2011; Hostein, 2010; Mayer, 2010; Honecker, 2009; Borger, 2012; Chapman, 2011a; Chapman, 2011b; Schonleben, 2009; Warth, 2011; Schindler, 2011]. These BRAF-mutated rare cancers have no effective treatment available either in the first-line setting for ATC, ASI and BRAF V600E-mutated GIST or in the refractory disease setting for NSGCT/NGGCT, BTC, WHO Grade 1 or 2 glioma, WHO Grade 3 or 4 glioma, HCL and MM. Therefore, there is a high unmet medical need for these rare cancer indications.

Table 1 Overall Incidence Rate and BRAF V600E Mutation Rate of Rare Cancers

Tumor Type	Overall Incidence Rate per 100,000 in US (2011)	BRAF V600E Mutation Rate (%)
Anaplastic Thyroid Cancer (ATC)	0.10	24%
Biliary Tract Cancer (BTC)	0.6	7 to 30%
Gastrointestinal Stromal Tumor (GIST)	0.7 to 1.1	2 to 5%
Germ Cell Tumor (GCT) (approximately 50% non-seminomatous)	6.31 (White males) 1.38 (Black males)	3%
World Health Organization (WHO) Grade 1 or 2 glioma	6.5	Approximately 7%
WHO Grade 3 or 4 glioma	2 to 4	Approximately 3% (glioblastoma [GBM])
Hairy Cell Leukemia (HCL)	0.33	90 to 100%
Multiple Myeloma (MM)	5.579	4%
Adenocarcinoma of the Small Intestine (ASI)	0.073	Approximately 10%

References: Caronia, 2011; Tiacci, 2011; Hostein, 2010; Mayer, 2010; Honecker, 2009; Borger, 2012; Chapman, 2011b; Schonleben, 2009; Warth, 2011; Schindler, 2011

It is expected that in some of these BRAF-mutated rare cancers substantial clinical activity of BRAF and MEK inhibition will be observed similar to that in metastatic melanoma (breakthrough efficacy). For most rare cancers, conventional drug development programs are not feasible due to the low incidence of disease and the limited commercial opportunities. These challenges may reduce the incentive to explore the potential benefit of new targeted therapies for rare cancers. An alternative and likely more feasible approach may be based on the detection of BRAF V600E mutations in these rare cancers as a common denominator for investigation of a BRAF + MEK inhibitor in such well-defined subject populations. Enriched Bayesian statistical designs and a high target effect size may enable meaningful clinical investigation of targeted therapies in these small patient groups.

A somewhat similar approach was taken with imatinib, where several label indications were granted by US FDA based on an open-label, Phase II clinical trial of imatinib in subjects with multiple rare tumor types associated with imatinib sensitive tyrosine kinases along with

published reports. The results of this one Phase II study in 186 subjects provided the basis for approvals in myelodysplastic/ myeloproliferative diseases, aggressive systemic mastocytosis, hypereosinophilic syndrome/chronic eosinophilic leukemia, and dermatofibrosarcoma protuberans. There were three responders out of seven subjects with myelodysplastic/ myeloproliferative diseases, one in five subjects with aggressive systemic mastocytosis, four out of 14 in the hypereosinophilic syndrome/chronic eosinophilic leukemia cohort and 10 out of 12 in the dermatofibrosarcoma protuberans cohort of that particular study [Heinrich, 2008]. It repeatedly appeared in the US FDA review of the submission for the extension of indication for Gleevec (2006) that “the (US) FDA medical reviewers recommended approval based on ‘long duration of responses’ and the rarity of disease and the occurrence of associated gene arrangement makes randomized trials impractical”.

While it is anticipated that several rare cancers with V600E mutations will have clinically substantial response rates of 50% or more to BRAF plus MEK inhibition, in some settings resistance mechanisms may prevent such high response rates. For example, the BRAFi vemurafenib and dabrafenib have shown response rates of greater than 50% in BRAF-mutant metastatic melanoma, but show substantially lower response rates in BRAF-mutant metastatic colorectal cancer based on resistance mechanisms through receptor tyrosine kinases (RTKs) [Prahallad, 2012]. This reaffirms that pathways of resistance may vary between histologic disease entities and underscores – in the absence of a full understanding of such mechanisms of resistance for all histologies – that individual assessment of histologic types remains a relevant component of the investigation together with adequate PD markers to understand them.

Therefore, a Phase II study is proposed to investigate BRAF-mutant rare cancers in individual cohorts defined by histology with the objective to demonstrate breakthrough clinical effects from combination therapy with dabrafenib + trametinib. To address the inevitable small sample sizes per histologic cohort, the study will utilize a Bayesian hierarchical statistical design, which increases the power of the overall investigation by borrowing information across histology cohorts based on the emerging rate of response in these cohorts. Pharmacodynamic markers will be evaluated to ensure we gain insights into the biology of each cancer type and also understand potential mechanisms of resistance.

2.3 Dose Rationale

Administration of dabrafenib + trametinib in the ongoing study BRF113220 indicates that dabrafenib does not have a clinically relevant effect on trametinib PK [GlaxoSmithKline Document Number CM2010/00010/05]. Cross-study comparisons indicate that exposure to dabrafenib may be greater after repeat-dose administration of dabrafenib in combination with trametinib relative to administration of dabrafenib alone at 150 mg BID. The combination was relatively well tolerated in study BRF113220, study MEK115306 and study MEK116513, with toxicities manageable with appropriate intervention.

In this study, dabrafenib will be administered at the dose of 150 mg BID continuously that demonstrated significant benefit in PFS in a Phase III trial [Hauschild, 2012]. Trametinib administered at a dose of 2 mg once daily has demonstrated significant benefit in PFS (hazard ratio [HR] = 0.45), a confirmed response rate (22% vs. 8%), and OS (HR = 0.54) relative to chemotherapy [Flaherty, 2012]. **As determined in Phase III studies, the safety profile of the combination of dabrafenib and trametinib generally reflects the well established**

safety profiles of the individual approved agents, with toxicities that are manageable with appropriate intervention.

2.4 Design Rational

Due to the common pathway activation with the BRAF V600E mutation, multiple histologies may demonstrate substantial response to BRAF plus MEK inhibition. However, pathways of resistance may vary between histologic diseases resulting in different responses to the targeted combination therapy.

This single-arm, multi-histology study incorporates analyses based on a hierarchical model that allows for the possibility that the response profile for the population of histologies may be homogenous or heterogeneous. There may be ‘clusters’, or subsets of histologies, some in which the combination therapy is effective, and others not. The design borrows information in a limited sense from histologies that demonstrate similar response rates based on the accumulated trial data. If response rates are sufficiently different across particular histologies, the design recognizes this and borrowing is minimal. The analysis is entirely data driven. The number of clusters used to characterize the distribution of histologies is solely based on the observed responses. At each interim analysis as well as the final analysis, the entire model including clustering specification is fit based on the available data.

Prospectively, the entire design including model specification and decision criteria is developed by evaluating its performance from simulated trials. Hence, the false-positive rate can be controlled and power assessed. The advantages of a hierarchical model, both due to borrowing, are 1) increased precision of estimates of ORR, and 2) more accurate estimates of ORR.

Borrowing via a hierarchical model analysis is a type of shrinkage estimation; it provides a formal mechanism by which extreme observations are shrunk toward the mean. Shrinkage estimators have long been supported by literature. In particular, Berry et al. [Berry, 2013] highlighted that in the 1950s, Charles Stein [Stein, 1956; James, 1961], under normality, demonstrated that when there are three or more groups, estimating the groups separately (without borrowing) is inadmissible in the sense that the mean squared error is improved uniformly by borrowing.

For all these reasons, borrowing information generally increases the power to detect a clinically meaningful ORR compared to a traditional analysis while controlling the type I error rate. Independent analyses do not consider the possibility that some of the histologic cohorts may respond similarly to the targeted combination therapy. And due to the rarity of the biomarker subtypes of the diseases being considered, a traditional approach will likely have difficulty accruing a sufficient number of subjects to have adequate power to detect even a very large treatment effect in several of the histologic cohorts.

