A hierarchical model that borrows information across cohorts will be utilized to strengthen the overall evidence within each cohort. Using the hierarchical model, continuous monitoring for both futility and efficacy will be undertaken throughout the study. Reviews will take place in approximately 12-week intervals depending on the enrollment rate. Enrollment for each cohort may be stopped early for futility or efficacy should various criteria occur based on accrued data. Response data from a minimum of five subjects will be required in a histologic cohort before it may discontinue enrollment for futility, and response data from a minimum of 10 subjects are required before discontinuing a histologic cohort for efficacy. In addition, at the final analysis and after the study has been closed, response data from a minimum of 2 subjects will be required in a histologic cohort in order to meet statistical success at the final analysis.

Decisions are based on whether the posterior probability that the ORR exceeds its corresponding historical control is sufficiently low or high compared to fixed statistical thresholds. Historical controls vary across histologic cohorts, but are all very low due to a lack of effective treatment options (Section 18.3.2.1). If this posterior probability is sufficiently low within a given histology (≤ 0.30), then enrollment may be halted early for futility. Conversely, if this posterior probability is sufficiently high within a given histology (≥ 0.95), then enrollment may be halted early for success. At the final analysis and after the study has been closed, if the posterior probability is sufficiently high (≥ 0.92), then the combination will be declared efficacious for that histology. Separate from model estimates, the observed ORR will also be reported for each histology. Further details regarding the statistical study design and analysis along with simulated example trials to illustrate the study may run is provided in Section 18.4.

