18.2 Sample Size Considerations

18.2.1 Sample Size Assumptions

Each cohort of BRAF V600E mutation-positive tumor type of a given histology will enroll a maximum of 25 subjects **in the primary analysis cohort as defined in Section 5.1**. If all histologies enroll the maximum of 25 subjects, this will result in no more than 225 subjects in the primary analysis cohort.

Enrollment into specific histology cohorts may be halted early based on results from interim analyses incorporating emerging response data. Response data from a minimum of 5 subjects will be required in a histologic cohort before it may discontinue enrollment for futility and response data from a minimum of 10 subjects will be required before discontinuing a histologic cohort for efficacy. **If a cohort closes early for efficacy at an interim analysis, a histology specific expansion cohort (see Section 5.2) may be opened to allow additional enrollment.** At the final analysis and after the study has been closed, a minimum of 2 subjects will be required in a histologic cohort in order to meet statistical success at the final analysis. See Section [18.3.2](#) for more details.

Simulation studies were conducted to evaluate the performance of the design under various assumptions for the distribution of true ORRs across the histologic cohorts and accounting for the anticipated small sample sizes (refer to Section [18.4.1.2](#)). Operating characteristics including power, type I error, estimation of the ORR, and the probability of halting enrollment at interim analyses were assessed.

When the treatment effects are similar across all histologies, the design maintains power 84% to 98% and type I error rate ≤ 0.04 . Estimation efficiencies due to borrowing result in very good operating characteristics in these situations, even in histologies with very low sample sizes.

In mixed scenarios where some histologies show large treatment effects and others do not, the type I error can range from 0.03 to 0.14 while the power ranges from 55%- 96%. This variation is hugely dependent upon the expected sample sizes of the individual histologies as well as the overall distribution of treatment effects across the histologies.

Full presentation and discussion of the simulation parameters and corresponding simulation results are in Section [18.4](#).

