18.3.2.2 Early Stopping for Efficacy

For each histology, the combination therapy will be declared efficacious and enrollment terminated if a minimum of 10 subjects have response data available and the posterior probability that the ORR exceeds its corresponding historical control (C_j) is sufficiently high (>95%) based on the hierarchical model. That is,

$$P(\pi_j > C_j \mid \text{current data}) > 95\%, \text{ for the } j\text{-th histology.}$$

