18.3.3.2 Efficacy Analyses

ORR will be analyzed using an integrated analysis with the hierarchical model as well as analyzed independently **for each histology**.

At the final analysis a histology will be declared active if the posterior probability that the ORR exceeds its corresponding historical control (10%) is sufficiently high (>92%) based on the hierarchical model. That is,

$$P(\pi_j > C_j \% \mid \text{current data}) > 92\%, \text{ for the } j\text{-th histology.}$$

The observed ORR and the estimated ORR based on the hierarchical model will be reported for each histology. Confirmed ORR will be calculated as the proportion of subjects that have a confirmed response relative to the total number of subjects enrolled. Standard response assessments vary by histology; the following subcategories for each histology will be considered a ‘response’ to therapy when computing confirmed ORR.

Table 31 Response Subcategories Defined as ‘Response’ by Histology

Histology	Response Criteria	Response Subcategories defined as ‘Response’
ATC, BTC, GIST, Small Intestine Adenocarcinoma	RECIST 1.1	CR, PR
NSGCT/NGGCT	RECIST 1.1. Tumor Markers: β -HCG and AFP	Marker-Negative CR, Marker-Positive CR, Marker-Negative PR, Marker-Positive PR
MM	IMWG Uniform Response Criteria for MM	sCR, CR, PR, VGPR
HCL	Adapted from NCCN guidelines, Consensus Resolution Criteria and previous studies definition	CR \pm MRD, PR
WHO Grade 1 and 2 Gliomas	Response Assessment Criteria for WHO Grade 1 or 2 Gliomas: RANO Working Group	CR, PR, MR
WHO Grade 3 and 4 Gliomas	Updated Response Assessment Criteria for WHO Grade 3 or 4 Gliomas: RANO Working Group	CR, PR
Abbreviations: AFP, alpha-fetoprotein; ATC, anaplastic thyroid cancer; β -hCG, beta-human chorionic gonadotropin; BTC, biliary tract cancer; CR, complete response; GIST, gastrointestinal stromal tumor; HCL, hairy cell leukemia; IMWG, International Myeloma Working Group; MM, multiple myeloma; MR, minor response;		

NCCN, National Comprehensive Cancer Network; NGGCT, non-geminomatous germ cell tumor; NSGCT, non-seminomatous germ cell tumor; PR, partial response; RANO, Response Assessment for Neuro-Oncology; RECIST, Response Evaluation Criteria in Solid Tumors; sCR, stringent complete response; VGPR, very good partial response; WHO, World Health Organization

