18.4.2 Operating Characteristics

18.4.2.1 Power and Type I Error Rate

[figure not shown]
Power and type I error rate are examined across scenarios for the distribution of assumed true ORRs for each histology. The power is the probability of declaring efficacy within a histology when the true underlying ORR is greater than its corresponding historical control. Type 1 error rate is the probability of declaring efficacy within a histology when the true underlying response rate is equal to the historical control. [Figure 1](#) illustrates the proportion of trials that declare each histology efficacious at the final analysis across simulation scenarios. Supporting tables for the simulation results are provided in [Appendix 7](#).

The power and type I error rate are dependent upon the sample sizes and response rates across the distribution of histologies. When the treatment effects are the same across all histologies (either all responsive or all non-responsive), estimation efficiencies, due to borrowing, result in very good operating characteristics, even in histologies with very low sample sizes. Under sample size Case 1, the type I error rate is controlled to ≤ 0.04 across all histologies (All Null scenario). The design maintains power 93% to 98% for the higher enrolling cohorts, and 84%

to 90% for the smallest enrolling 5 cohorts (All Great scenario). Also, the design exhibits reasonable power to detect a moderate level of activity (All moderate scenarios).

When the treatment effects vary across histologies, the amount of appropriate borrowing also varies, impacting the operating characteristics. The ‘2 Greats: Mixed’ investigates design performance where most histologies are not responsive. In this situation, the type I error rate is controlled to ≤ 0.06 and the power is 82% for the higher enrolling cohort and 55% for the low enrolling cohort. The ‘5 Greats: Mixed’, ‘5 Greats: Low’ and ‘Mixed’ scenarios investigate the design performance in situations where roughly half the histologies are responsive. The type I error rate ranges from 0.09 to 0.14 while the power ranges from 93% to 96% for the higher enrolling cohorts and ranges from 67% to 84% for the lower enrolling cohorts. Generally, improvement in the overall distribution of treatment effects tends to coincide with slight increases in type I error rate and moderate increases in power.

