18.4.2.3 Probability that the Model Declares Success Across Different Sample Sizes

To evaluate the model performance for various sample sizes, simulations are also performed under the following four scenarios for sample sizes specified in Case 2, 3, and 4 with the maximum sample size for a given histology can be as high as 25.

Table 34 Simulation Scenarios for Enrollment Sensitivity: Various Assumptions for the True ORR for Each Histology

Scenario	Histology								
	1	2	3	4	5	6	7	8	9
Mixed1	20%	30%	60%	30%	40%	40%	10%	15%	75%
5 Greats: Mixed1	10%	50%	60%	50%	10%	50%	10%	15%	75%
4 Greats: Low	10%	10%	15%	50%	10%	50%	50%	15%	75%
2 Greats: Mixed1	10%	10%	60%	10%	10%	10%	50%	15%	25%

When the sample size for some histology increases from 15 to 25, the largest type I error increases from 0.14 to 0.18. Under sample size Case 2, the type I error rate is ranges from 0.04-0.17; the design maintains power 94% to 98% for the higher enrolling cohorts (>10 subjects enrolled per cohort), and 61% to 87% for the smallest enrolling three cohorts (5 subjects enrolled per cohort). Under sample size Case 3, the type I error rate is ranged from 0.04 to 0.18; the power is ranged from 92% to 98% for high enrolling cohorts (>10 subjects enrolled per cohort) and ranged from 62% to 86% for low enrolling cohorts (5-8 subjects

enrolled per cohort). Under sample size case 4, the type I error ranges from 0.02 to 0.16; the power ranges from 93% to 96% for high enrolling cohorts (>10 subjects enrolled per cohort), 59% to 71% for low enrolling cohorts (5-8 subjects enrolled per cohort) and 26% to 44% for ultra low enrolling cohorts (2 subjects enrolled per cohort). [Figure 4](#) illustrates the proportion of trials that declare success across all possible combinations of sample sizes and number of observed responses and for each historical control response rate. Supporting tables for the simulation results are provided in [Appendix 7](#).

Also, the design exhibits reasonable power to detect a moderate level of activity. The type I error rate maintains well under different sample size scenarios and reasonable power are achieved for cohorts which enroll no less than 5 subjects per cohort. The powers for cohorts that have super low enrollment (n=2 or less) can be lower than 50%. Overall the design performance is robust to overenrolling up to 25 subjects for a given histology.

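### Section 2.4 claims type I error control without figures; one ineffective histology among eight responsive ones, a case not simulated, has a false-positive rate of about 0.15–0.21 in Case 1, above the stated 0.03–0.14

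*Protocol*

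**What the plan says.** Section 2.4 of the protocol gives the case for the hierarchical model: "borrowing information generally increases the power to detect a clinically meaningful ORR compared to a traditional analysis while controlling the type I error rate". It names no target error level. It also says: "If response rates are sufficiently different across particular histologies, the design recognizes this and borrowing is minimal".

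The final rule (protocol Section 18.3.3.2, SAP 2.4.2) declares a histology active when the posterior probability that its ORR exceeds its historical control is above 92%. The cohort can be very small: "a minimum of 2 subjects will be required in a histologic cohort in order to meet statistical success at the final analysis" (Section 18.2.1). SAP 4.11 makes no multiplicity adjustment.

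Section 18 reports how the error moves:
- at most 0.04 when every histology is at control;
- at most 0.06 when two respond;
- when about half respond, "The type I error rate ranges from 0.09 to 0.14" (Section 18.4.2.1).

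Section 18.2.1 summarises the mixed scenarios as 0.03 to 0.14 and does not limit that range to Case 1. Section 18.4.2.3 goes further: "When the sample size for some histology increases from 15 to 25, the largest type I error increases from 0.14 to 0.18".

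**The concern.** In Section 18 the error rises as more histologies respond. The end of that trend is one ineffective histology with every other one responsive, where the pull on the ineffective cohort should be strongest. If that point was not simulated, the stated maxima are not maxima, and the sentence in Section 2.4 rests on a set of scenarios that stops short.

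Each histology gets its own declaration. If the treatment works in most tumours, the remaining cohort is the one most exposed to a false declaration. If that cohort is also tiny, the declaration may rest mainly on other tumours' data. The planned SAP table would not show that this had happened.

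**Working it through.** **Inputs.** Appendix 6: Dirichlet process with parameter 2; cluster mean N(0, 3), with 3 read as a variance; τ² ~ IG(3, 0.5) per cluster; logit offset at the historical control. Table 32: control and target rates (10%/50% for six histologies, 15%/60% for ATC and MM, 25%/75% for NSGCT/NGGCT) and projected enrolment. Section 18.3.2: futility below 0.30 with n ≥ 5, efficacy above 0.95 with n ≥ 10. Final rule above 0.92 with n ≥ 2. Section 18.4.1: looks every 12 weeks from 10 enrolled, 8-week response lag, 156 weeks. Poisson accrual is assumed.

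**1. Does the reconstruction match the protocol?** Summing over all partitions of the nine histologies reproduces all 54 final decisions in Appendix 8. Posterior probabilities differ by at most 0.026 and estimated ORRs by at most 0.011. For Case 1:

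| Quantity | Protocol | Reconstruction |
|---|---|---|
| Null, largest type I error | ≤ 0.04 | 0.035 |
| Alternative, power | 84–98% | 83.7–98.1% |
| Mixed and 5 Greats, type I error | 0.09–0.14 | 0.08–0.12 |
| 2 Greats, type I error | ≤ 0.06 | up to 0.067 |
| 2 Greats, power | 82% / 55% | 86% / 59% |

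The homogeneous scenarios match. The mixed ones are close but not exact. In the half-responsive scenarios the reconstruction gives a slightly lower error than the protocol.

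**2. Which scenarios were run?** Number of histologies at their control rate:
- Table 33: Alternative 0, Null 9, All Moderate 0, Mixed 2, 5 Greats: Mixed 4, 5 Greats: Low 4, 2 Greats 7.
- Table 34: Mixed1 2, 5 Greats: Mixed1 4, 4 Greats: Low 5, 2 Greats: Mixed1 7.

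None has exactly one. In Mixed and Mixed1, only two of the seven other histologies are at the clinically meaningful rate.

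**3. One null, eight at target.** Case 1, 2,500 trials per histology (SE about 0.008), histologies 1 to 9 in turn: 0.150, 0.155, 0.152, 0.164, 0.175, 0.178, 0.183, 0.171, 0.212. The range is 0.15–0.21. Without interim looks, at Case 1 sizes, the spread is about 0.11–0.22. Cases 2–4 with interims, from smaller runs (400–1,500 trials per cell, SE about 0.01–0.02), give about 0.11–0.22.

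**4. Cohorts ending with 2, 3 or 4 subjects, 10% control.** Let s be the probability that a single response meets the 92% rule when the other eight respond. No response never succeeds, and two or more are counted as success. Then type I error = s·P(Y = 1) + P(Y ≥ 2).
- n = 2: s = 1.00; 1 − 0.9² = 0.19.
- n = 3: P(Y = 1) = 3(0.1)(0.81) = 0.243; P(Y ≥ 2) = 0.028; s = 0.993 (Case 1); 0.993 × 0.243 + 0.028 = 0.269.
- n = 4: P(Y = 1) = 4(0.1)(0.729) = 0.292; P(Y ≥ 2) = 0.052; s = 0.801 (Case 1) to 0.945 (Case 3), giving 0.286 to 0.328.

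The other controls behave differently because the counts are so coarse. At n = 2, 3, 4 in Case 1, a 15% control gives 0.28, 0.31, 0.11 and the 25% control gives 0.38, 0.16, 0.26. Over all controls and cases the range is 0.11–0.42.

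**5. The same rule without borrowing** (same prior, cohort alone). At n = 2, 3, 4:
- 10% control: 0.010, 0.028, 0.052;
- 15% control: 0.022, 0.061, 0.012;
- 25% control: 0.062, 0.016, 0.051.

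At n = 5, 8, 10 and 15 it runs from 0.02 to 0.10.

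**6. The protocol's own illustration.** In Appendix 8, 2/7 against a 10% control is a success at 0.98 in Example 1 (histology 2) and a failure at 0.88 in Example 4 (histology 4). Only the other cohorts' data differ.

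**7. A discrepancy in the benchmark.** In Mixed1, Table 34 sets histology 8 at its 15% control, yet Appendix 7 prints 0.47–0.50 for it. Histology 1 is set at 20%, above its 10% control, and prints 0.16–0.18. The stated maximum of 0.18 appears in Appendix 7 only in that histology 1 column (Case 3). Rerunning Cases 2 and 4 gives 0.15–0.16 for histology 8 and 0.51–0.54 for histology 1, so the columns look exchanged.

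**The case against.** A reader might infer that ineffective histologies among responsive ones were never simulated, or that the inflation was hidden. The documents support neither. Mixed, both 5 Greats scenarios and Mixed1 contain such histologies. Section 18 reports errors up to 0.18, states that the error rises as the overall treatment effects improve, and says in 18.4.2.2 that one response can succeed when n is roughly 5 or fewer.

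Other points on that side also stand:
- The sentence on minimal borrowing is conditional on rates being sufficiently different. A cohort at 1/2 or 1/3 does not look different from responsive ones, so the sentence is not contradicted.
- Section 2.4 says borrowing helps generally, and no nominal level exists to be breached.
- Section 2.2 expects several cancers to respond, not most, so the one-null case is a bounding case rather than the expected one.
- Sections 18.4.2.2 and Appendix 8 ask for the totality of the data as well as statistical success.
- Enrolment ended in June 2018, so new simulations cannot alter the design.
- Part of Section 18.4.1 is redacted, so the accrual model is an assumption.

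Two arguments do not remove the point. The exact confidence intervals planned in the SAP show imprecision, but not whether the 92% rule would be met without borrowing. And a correct error rate still affects how each histology's declaration is read after enrolment has closed.

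**Conclusion.** The point holds as an overstated sentence in Section 2.4, an understated range in Section 18.2.1 and one missing bounding scenario. In Case 1 the one-null error of about 0.15–0.21 exceeds the stated 0.14 for every histology. In Cases 2–4, at about 0.11–0.22, it passes the stated 0.18 only at the upper end, and that range has the larger simulation error.

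The small-cohort figures of 0.19, 0.27 and 0.29–0.33 apply to 10%-control cohorts only. It is tempting to quote 1 − 0.9⁴ = 0.34 at n = 4, but that is an upper bound that assumes a single response always wins.

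The results assume Poisson accrual, N(0, 3) as a variance, and re-evaluation of futility-stopped cohorts at the final analysis. Treating those stops as binding moves the rates by about 0.01 or less.

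**What to change.** 1. Add the scenario with one histology at control and eight at the clinically meaningful rate, for Cases 1–4, taking each histology in turn as the null. Restate the largest type I error in Sections 18.2.1 and 18.4.2, with separate values for cohorts that end with 2, 3 or 4 subjects.
2. In Section 2.4, replace the closing clause on type I error control with the actual range. The conditional sentence on minimal borrowing can stay.
3. In the SAP 2.4.2 model table, add the posterior probability computed without borrowing (same prior, that cohort alone) and flag any success reached only through borrowing.
4. During the rerun, reconcile Table 34 with Appendix 7 for Mixed1, histologies 1 and 8.

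The cost is one more simulation run, revised wording and one extra column. The stated error rate becomes less favourable.
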